- 402 2002 onward, all of whom will be >2 years post-donation at re-enrollment, enriched by the addition
- 403 of (b) all living liver donors >2 years post-donation recruited from the new A2ALL-2 sites
- 404 (Pittsburgh, Toronto, Lahey). This enriched cohort will receive a "baseline" assessment at time of
- 405 (re)contact, and they will be surveyed annually for the next 3 years in order to achieve the following406 objectives:

407 **3.3.1 Objectives – Long-term donor follow-up cohort**

To determine the prevalence and course of change in poor HRQOL outcomes in five domains during the extended years after donation:

410	• Clinically significant psychiatric symptomatology related to depression and
411	anxiety
412	• Enduring fatigue, other somatic symptoms, and lasting health concerns
413	• Negative changes in relationships with the transplant recipient and/or other family
414	members
415	• Financial strains related to health-related expenses and to changes in employment,
416	and health-, Disability- or life-insurance benefits.
417	 Reductions in global/overall HRQOL
418	• To determine the prevalence and course of change across time in positive psychological
419	outcomes of donation, including satisfaction with donation and personal growth related to
420	the experience.
421	• Among donors followed since donation, to examine whether pre-donation characteristics
422	(e.g., demographics, motivations and ambivalence about donating) and medical factors
423	(e.g., perioperative complications) predict poor HROOL at baseline and predict
424	persistently impaired HROOL across the study period.
425	3.3.1.1 Hypotheses:
426	In the long-term years post-donation:
427	• the prevalence of poor HRQOL outcomes at initial follow-up contact will be higher than the
428	rates of these problems in normative (population-based) samples,
429	• based on studies in kidney donors, we hypothesize that ~30% of liver donors will experience
430	clinically significant (above-threshold) HRQOL impairment at initial follow-up contact.
431	• Concerning course and predictors of HRQOL:
432	• on average across the follow-up assessments, we expect that donors who have
433	clinically significant HRQOL impairment at baseline will be likely to continue to
434	show such impairments over time
435	• we also expect the differences between "screen positive" and "screen negative"
436	donors will grow smaller with time, i.e., the rates of some problems, e.g., financial

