*most of the measures and items are copyrighted and are reproduced with permission **depending on whether respondent skips out of sections

***estimate based on pilot testing

781 We anticipate a total sample size of 300 donors from the existing A2ALL cohort, enriched with 300

additional donors from the new A2ALL sites (Total N = 600). This sample size estimate is based on

- the sampling frame requirements described above, an assumption that we will be unable to locate
- 10% of donors despite using state-of-the-art internet-based search strategies for donors lost to follow
- up at centers, and an assumption that 20% to 30% of donors recontacted will refuse to provide
 consent for a long-term follow-up study. Furthermore, across 3 years of follow-up, we anticipate
- consent for a long-term follow-up study. Furthermore, across 3 years of follow-up, we anticipate
 (based on our past experience in following transplant-related samples using the type of survey)
- 788 strategies described earlier), that attrition will range between 10% to 15%.
- 789 With a sample of 600 donors at the initial assessment, our power to detect whether the rate of poor
- HRQOL in the donors differs from a population/normative rate (at alpha < .05, two-tailed) exceeds
- .995, even for very small differences of less than 2% between the observed and normative rates
- 792 (Specific Aim 2, Objectives a.1. and a.2.). For hypotheses focused on specific effects or
- relationships, our power exceeds .80 at alpha = .05, two tailed, for moderate-sized⁶⁸ effects even if as
- much as 50% of the sample is lost to attrition (a percentage much higher than expected, as noted
- above). We note that we will not restrict our analyses to consideration of outcomes at only individual time points but will utilize a mixed effects approach (which is appropriate both for interval and
- time points but will utilize a mixed effects approach (which is appropriate both for interval and discrete outcomes). Power will be even greater under a mixed effect approach because such models
- allow for the inclusion of cases with incomplete data, and thus our effective sample size will be the
- total cohort enrolled. Therefore, even if we apply corrections for multiple comparisons (given the
- fact that we will examine multiple domains of HRQOL), our power will continue to exceed .80 for
- 801 examining relationships such as risk factor-outcome associations.

802 4.3.4 Sample size and power calculations

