Total No. of items/duration of assassment	0, 21-23, 24a-1, 23, 20a-d	136 to 166/**
rotar no. or items/duration or assessment		24 to 38
		min***

depending on whether respondent skips out of sections *estimate based on pilot testing

- 878 For the prospective donor cohort HRQOL studies at 1 year and 2 years post-donation, the
- assessments are identical to those at 3 months and 6 months in the prospective cohort, except that the
- 880 10-item Posttraumatic Growth Inventory is included. This will increase the estimate time to 26 to 40
- 881 minutes.

882 **4.3.9** Sample size and power calculations

883 We anticipate a total sample size of 375 liver donors. This sample size estimate is based on the numbers of living liver donor transplants performed at A2ALL-2 sites during the past 3 years and the 884 885 expectation that we would enroll subjects for a total of two years going forward (allowing for follow-up of the last subjects enrolled before the end of A2ALL-2 funding). It also assumes 20% to 886 887 30% of prospective donors will refuse to enroll. Finally, across the study period, we assume that 888 attrition will range between 10% to 15% (based on our past experience with donor and other 889 transplant-related samples using the type of survey strategies proposed). Thus, by the final 890 assessment wave, we expect to have a sample of 319 to 337 liver donors.

- 691 Given expected refusals to enroll and expected attrition, even with 319 liver donors (the worst-case
- scenario) we would have power exceeding .995 to detect small differences of less than 4% between a
- 893 "case" rate of problems in a given HRQOL domain (e.g., rate of clinically significant psychiatric
- symptomatology) and a population/normative rate (Primary Aim 2, Objectives b.1. and b.2.). For
- 895 Objective b.3., we would utilize the same strategies as those described for the long-term follow-up 896 cohort. With a sample of 319, utilizing a regression approach to examine donor outcome status at a
- given time point (see also Section 4.3.10 below), with two-tailed alpha at .05, as many as 8
- 898 covariates controlled, and allowing the covariates themselves to have moderate-sized associations
- 899 with the outcome, then our power to detect even conventionally small⁶⁸ differences in proportions or
- 900 means will exceed .80. We note that we will not restrict our analyses to consideration of outcomes

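### Power above .995 for differences under 2 points (n=600) or under 4 points (n=319) from a normative rate is not what these samples give: with rates near 30% it is about 0.2 and 0.35

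*Protocol*

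**What the plan says.** The long-term cohort's power text stands at the end of Section 4.3.3, after Table 1. It takes 600 donors at the first assessment and a two-sided test at .05 against a fixed norm, puts power above .995, and says that this applies "even for very small differences of less than 2% between the observed and normative rates". Section 4.3.4, which is headed as the sample size section for this cohort, says only that it does not apply. The text in 4.3.3 is therefore the cohort's only power statement.

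For the prospective cohort, Section 4.3.9 takes 319 donors as the least favourable number after losses. Its claim reads: "we would have power exceeding .995 to detect small differences of less than 4% between a". The two rates compared there are again the donors' rate of cases in an HRQOL domain and a norm.

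Neither section gives a normative rate. The only anticipated rate is in Section 3.3.1.1, for the long-term cohort: "based on studies in kidney donors, we hypothesize that ~30% of liver donors will experience". The outcome meant is impairment above the clinical threshold when donors are first contacted. The same list hypothesises that donor rates will lie above the norms.

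**The concern.** Sample size, alpha, sidedness, comparator and difference are all given, so the claim can be checked. At two-sided .05, power of .995 needs a true difference of about 1.96 + 2.58 = 4.54 standard errors. With 600 donors and rates near 30%, one standard error is about 1.9 points, so 2 points is only about one standard error.

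Comparison with norms is the first hypothesis listed for the long-term cohort, and Sections 4.3.5 and 4.3.10 plan it for both cohorts. A reader who trusts the stated power would take a non-significant comparison as ruling out an excess of 2 points (or 4 points) over the general population. In fact, at norms of 20% to 30%, a true 2-point excess would be missed about four times in five with 600 donors. That would be false reassurance in research meant to inform future donors.

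**Working it through.** **Inputs.** n = 600, two-sided alpha .05, difference under 2 points, power above .995 (Section 4.3.3). n = 319, which is 375 less 15% attrition (375 × 0.85 = 318.75), difference under 4 points, power above .995 (Section 4.3.9). Expected donor rate about 30%, long-term cohort only (Section 3.3.1.1). The normative rate p0 is not given, so it is assumed over a range. The difference is set at the full 2 or 4 points, the most favourable reading, because smaller differences have less power.

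**Formula.** One-sample test of a proportion against a fixed rate p0, with true donor rate p1:

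power ≈ Φ( [ |p1 − p0| − 1.96 √(p0(1−p0)/n) ] / √(p1(1−p1)/n) )

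**Numbers put in at a 30% norm.**

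- n = 600, 30% vs 32%: √(0.30×0.70/600) = 0.0187 and √(0.32×0.68/600) = 0.0190. (0.02 − 1.96×0.0187)/0.0190 = −0.88, so power is 0.19.
- n = 319, 30% vs 34%: √(0.30×0.70/319) = 0.0257 and √(0.34×0.66/319) = 0.0265. (0.04 − 1.96×0.0257)/0.0265 = −0.39, so power is 0.35.

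If 30% is instead the donor rate, the normal formula gives 0.20 for 28% vs 30% (n=600) and 0.38 for 26% vs 30% (n=319).

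**Exact binomial power of the same two-sided score test, donors above the norm.**

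| Norm | n=600, +2 points | n=319, +4 points |
|---|---|---|
| 0.5% | 0.993 | 0.999 |
| 1% | 0.971 | 0.997 |
| 2% | 0.88 | 0.971 |
| 5% | 0.59 | 0.85 |
| 10% | 0.37 | 0.63 |
| 20% | 0.23 | 0.45 |
| 30% | 0.18 | 0.36 |

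**Can the stated .995 be reproduced?** Only at very low norms. Depending on the method (score, arcsine or exact), the highest norm that gives .995 is roughly 0.3% to 0.5% for n=600 and 0.7% to 1% for n=319. Other readings do not help:

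- One-sided testing at a 30% norm gives 0.29 and 0.47.
- Using all 375 enrolled donors instead of 319 gives 0.40.
- A two-sample formula gives 0.12 (28% vs 30%, 600 per group) and 0.20 (26% vs 30%, 319 per group).
- Donors below the norm: 5% vs 3% with n=600 gives 0.64. This direction reaches .995 only when the donor rate is close to zero, and it contradicts the hypothesis of higher donor rates.
- A conventionally small effect (Cohen's h = 0.2) gives 0.998 at n=600 but 0.947 at n=319. At a 30% norm it is about 9 points, not 2 or 4.

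**Differences these samples can detect (points above the norm).**

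| Norm | n=600, 80% power | n=319, 80% power | n=600, .995 | n=319, .995 |
|---|---|---|---|---|
| 5% | 2.7 | 3.8 | 4.9 | 7.1 |
| 10% | 3.7 | 5.1 | 6.3 | 8.9 |
| 20% | 4.8 | 6.4 | 7.9 | 11.1 |
| 30% | 5.4 | 7.3 | 8.8 | 12.2 |

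The 80% columns use exact power, and the normal formula agrees to within about 0.1 point. The .995 columns use the normal formula.

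**Sample size the claims would need.** n = [ (1.96 √(p0(1−p0)) + 2.576 √(p1(1−p1))) / (p1 − p0) ]². For 30% vs 32% this is [(0.898 + 1.202)/0.02]², about 11,000 donors. For 30% vs 34% it is about 2,800.

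**The case against.** Five points can be made for the protocol.

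1. **The sample sizes do not rest on this power figure.** The 600 comes from the sampling frame, location and refusal rates; the 375 comes from past transplant volume and the enrolment window. Correcting the sentences changes no enrolment, visit or test. This is true and keeps the remedy to wording, but the stated sensitivity is still wrong.
2. **The hypothesised comparison may be well powered.** The 30% is the expected donor rate, and the norm could be much lower. With donors at 30%, power is above 0.999 (n=600) and 0.99 (n=319) against a norm of 20%, 0.99 and 0.87 against 22.5%, and 0.80 and about 0.55 against 25%. This stands: large excesses would be found. What fails is the claim about 2 and 4 points.
3. **No norm is stated, and rare diagnoses might have very low norms.** At a 1% norm the n=319 claim holds (0.997). But both sentences are worded for poor HRQOL in general, and the domains include depression, anxiety, fatigue, pain and financial strain. A norm below 1% does not fit that set.
4. **The 30% is given for the long-term cohort only.** Using it for the prospective cohort is an extension. The conclusion does not depend on it, since power at n=319 is already 0.85 at a 5% norm.
5. **The protocol does not say that non-significance will be read as equivalence.** That is so. The risk lies in how readers will use a stated power of .995.

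**Conclusion.** The concern holds. Both power statements are wrong as written for any normative rate above roughly 0.5% (n=600) or 1% (n=319). With rates near 30%, true power is about 0.2 for 2 points with 600 donors and about 0.35 for 4 points with 319. This assumes a one-sample comparison with a fixed norm, two-sided alpha .05 (stated for the long-term cohort and carried over to the prospective one) and the full stated difference. Anything smaller has less power. The norms are assumed over a range because the protocol gives none, but across 5% to 30% neither claim comes near .995: the best values are 0.59 and 0.85. Adequate power for a wide excess over the norm is not in dispute.

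**What to change.** In Sections 4.3.3 and 4.3.9, delete both claims of power above .995. State instead the difference detectable at 80% power by normative rate: for n=600, 2.7, 3.7, 4.8 and 5.4 points at norms of 5%, 10%, 20% and 30%; for n=319, 3.8, 5.1, 6.4 and 7.3 points. Name the norm assumed for each main HRQOL domain so that a reader can find the relevant row. Add that each prevalence will be shown with its confidence interval beside the norm, so that a non-significant result is not read as agreement with it.

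Check the prospective figure against Section 4.6.1.6, which anticipates about 200 future donors. At n=200, power for 4 points over a 30% norm would be about 0.25.

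The cost is protocol wording only. Enrolment, assessments and analyses stay as they are.

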8.1 APPENDIX A: Donor schedule of events

 \ast Old donors from new sites will not be getting labs or non-HRQOL-related study visits.

** All new donors from all sites.

***Can be collected at any timepoint during the study.

SUBJECTS JOINING THE STUDY FROM THE PREVIOUS A2ALL COHORT STUDY WHO ARE MORE THAN 4 YEARS POST-TXP WILL FOLLOW AN ANNUAL SCHEDULE OF EVENTS WITH THE SAME ASSESSMENTS AND SAMPLES AS YEAR 4.

Event										٦	'ime Poir	nt																
	Pre-TXP				At TXP												Post 1	ХР										
	Shortly Pre-TXP	Pre- op	After Portal Dissection	Back Table	After completion of the arterial anastomosis	After portal flow modification*	1° Post Reperfusion	Day 1	Day 2	Day 3	Day 4*	Day 5*	Day 6*	Day 7	Day 8*	Day 9*	Day 10*	Day 11*	Day 12*	, C	Day 13*	Wk 2	Mon 1	Mon 3	Yr 1	Y r 2	Yr 3	Y r 4
LFTs	х							X	Х	X	X	Х	X	Х	х	X	X	Х	X		X	Х	х	х	X	X	х	Х
CBC	X							X	X	X	X	Х	X	х	х	X	X	X	X		X	Х	х	x	X	X	х	X
Serum Creatinine	x							x	x	x	x	x	x	x	x	x	x	x	x		x	x	х	x	x	x	х	x
PT/INR	x							X	X	x	X	х	X	х	х	x	X	х	x		x	х	х	х	x	x	х	x
Sodium	Х							X	Х	х	х	Х	х	х	х	X	X	х	X		X	Х	х					
BUN	х							x	x	x	х	х	x	х	х	x	x	х	x		x	х	х					
HCV RNA																											X ***	
Pressure & Flow Measurements			x		x	x																						
Doppler Portal Vein Flow Rate								x																				
CT/MRI	x																							x				
Liver Bx -																												
Biorepository				X			X																				X ***	_
Whole Blood – DNA BioRepository	X**																										L	
Serum - Biorepository	x													x								x	х	x	x	x	x	x
Plasma & Peripheral Cells - Biorepository	x																						x	x	x	x	HCV Plasma Only	
Whole Blood - RNA Extraction for future study	x																						x	x	x	x		

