8.4 APPENDIX D: Potential Subjects for Enrollment into the Core Protocol

occurred in the Gap Era**(must be three years post-transplant for the HCV Study)						
New Subjects (all centers)	Enroll into Core Protocol?	Enroll into HRQOL Sub- study?	HCV Study	Donor Pain Study	Existing Data Sources	Potential Data Entry Methods
Actual Donors shortly Pre-donation	YES	YES	NO	YES	NONE	New Data Entry
LDLT Recipients shortly Pre-transplant	YES	NO	NO	NO	NONE	New Data Entry
Donors whose donation occurred in the Gap Era**	YES	NO	NO	NO	NONE	Upload/New Data Entry
LDLT Recipients whose transplant occurred in the Gap Era**(must be three years post-transplant for the HCV Study)	YES	NO	YES	NO	NONE	Upload/New Data Entry
Donors that Donated Prior to the Gap Era** (new centers only)	NO	YES	NO	NO	NONE	Upload/New Data Entry
LDLT Recipients whose transplant occurred during the Cohort Era****	NO	NO	YES	NO	NONE	Upload/New Data Entry
DDLT Recipients with HCV whose transplant occurred during the Cohort Era**** AND had a living donor evaluated(must be three years post- transplant for the HCV Study).	NO	NO	YES	NO	NONE	Upload/New Data Entry

* End of Cohort Enrollment = August 31, 2009

** Gap Era = September 1, 2009 - Site Initiation for Core Protocol (will vary by site)

*** Data for former A2ALL subjects exists in BioDBx up through August 31, 2010. All subjects will be post-

transplant/donation. Additional data for the time period September 1, 2010-Site Initiation for Core Protocol will have to be manually entered or uploaded via spreadsheet.

****Cohort Era = March 1, 2003 – Sept. 1, 2010

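### For pre-donation predictors, the long-term donor cohort's power is argued from 600 donors when at most about 300 can enter the analysis

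*Protocol*

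**What the plan says.** The power text for the long-term cohort stands at the end of Protocol section 4.3.3, after Table 1. It makes four statements that matter here.

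- Size: "We anticipate a total sample size of 300 donors from the existing A2ALL cohort, enriched with 300" more from the new sites, 600 in all.
- Attrition: the plan expects "that attrition will range between 10% to 15" per cent over three years.
- Power under heavy loss: for hypotheses about specific effects, "our power exceeds .80 at alpha = .05, two tailed, for moderate-sized" effects, even if as "much as 50% of the sample is lost to attrition (a percentage much higher than expected, as noted" in the same section).
- Power after correction: mixed models "allow for the inclusion of cases with incomplete data, and thus our effective sample size will be the" full cohort. From this the text infers that power remains above .80 for associations between risk factors and outcomes, even with a correction for examining several domains.

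The predictor objective in section 3.3.1 opens: "Among donors followed since donation, to examine whether pre-donation characteristics" and medical factors predict poor HRQOL. The hypotheses in 3.3.1.1 name ambivalence about donating and perioperative complications.

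On the new-site donors, the Appendix A footnote says: "Old donors from new sites will not be getting labs or non-HRQOL-related study visits". The Appendix D row "Donors that Donated Prior to the Gap Era" (new centers only) marks them as not in the core protocol, in the HRQOL substudy, with no existing data source, and with data entry by upload or new entry. The aims-by-era table in section 3 nevertheless lists the same donors under Aim 1 as well as Aim 3.

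**The concern.** Two different kinds of missing data are treated as one. A mixed model can use a donor who missed some follow-up surveys, because the remaining outcome waves still contribute. It cannot use a donor who has no value for the predictor under study. New-site donors are first contacted more than two years after donation. Their survey battery (Table 1) has no ambivalence, motivation or decision-making items; those appear only in Table 2, the pre-donation battery of the prospective cohort.

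The plan's own objective already excludes donors not followed since donation, so the power paragraph rests on up to twice the sample its objective allows. A reader who takes 600 at face value would give a null result for a pre-donation risk factor more weight than the data can bear.

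**Working it through.** **Inputs from the Protocol.** N = 600 = 300 + 300; two-sided alpha .05; power above .80; a moderate effect; 50% loss as the extreme case; 10% to 15% expected attrition (all 4.3.3); five HRQOL domains (3.3.1).

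**Assumptions, because the Protocol gives no figure.** Moderate is d = 0.5 for a binary risk factor or r = 0.3 for a continuous one. The correction is Bonferroni over five domains, alpha .05/5 = .01. Risk-factor prevalence f is varied over 50%, 30%, 20% and 10%.

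**Usable sample for pre-donation predictors.** At most 600 − 300 = 300. After 10% attrition 300 × 0.90 = 270; after 15%, 300 × 0.85 = 255; after 50%, 300 × 0.50 = 150.

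**Formulas.**
- Binary factor: non-central t with N − 2 degrees of freedom and non-centrality d × √(N f (1 − f)).
- Continuous factor: Φ(atanh(r) × √(N − 3) − z), with z = 1.960 at alpha .05 and 2.576 at alpha .01.

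**The plan's own figures first.** Half of 600 is 300.

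| Basis | f = 50% | 30% | 20% | 10% |
|---|---|---|---|---|
| N = 300, alpha .05 (50% loss from 600) | 0.991 | 0.977 | 0.932 | 0.736 |
| N = 600, alpha .01 (correction, full cohort) | 1.000 | 0.999 | 0.990 | 0.862 |

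On a base of 600 both statements reproduce, except for a 10% risk factor under 50% loss.

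**The same statements on a base of 300.**

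| Basis | f = 50% | 30% | 20% | 10% |
|---|---|---|---|---|
| N = 150, alpha .05 (50% loss) | 0.860 | 0.796 | 0.682 | 0.446 |
| N = 300, alpha .01 (correction, no loss) | 0.958 | 0.915 | 0.808 | 0.503 |
| N = 270, alpha .01 (10% attrition) | 0.934 | 0.878 | 0.755 | 0.450 |
| N = 255, alpha .01 (15% attrition) | 0.918 | 0.855 | 0.725 | 0.422 |
| N = 255, alpha .05 (no correction) | 0.978 | 0.954 | 0.889 | 0.665 |

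Examples of the non-centrality: N = 150, f = 30% gives 0.5 × √31.5 = 2.81; N = 255, f = 20% gives 0.5 × √40.8 = 3.19.

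**Sample needed for .80 at alpha .01** (normal approximation, (2.576 + 0.842)² / (f(1 − f) × 0.25)): 187, 223, 292 and 520 for f = 50%, 30%, 20% and 10%. The expected 255 to 270 donors exceed the first two and fall short of the last two.

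**Continuous predictor, r = 0.3** (atanh = 0.3095): at N = 150 and alpha .05, 0.3095 × √147 − 1.960 = 1.79, power 0.96. At N = 255 and alpha .01, 0.3095 × √252 − 2.576 = 2.34, power 0.99.

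**The case against.** The strongest reply is that the restriction is already in section 3.3.1, so nobody proposes to analyse predictors that do not exist, and that power remains good with 300 donors. Much of this stands. At expected attrition without correction, power is 0.89 or more for factors present in at least 20%. If all 300 contribute through the mixed model, the correction claim survives down to a 20% factor (0.81). Ambivalence can be analysed as a score, and a continuous predictor with r = 0.3 passes throughout. None of this rescues the stated basis, which is the full cohort, used explicitly to support the risk-factor claim.

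Three stronger readings are tempting, and the documents do not support them.

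- A reader might infer that the plan promises power above .80 under 50% loss and correction together. It makes two separate statements: the loss statement is at alpha .05, and the correction statement rests on the full cohort. The combined case (n = 150, alpha .01: 0.67, 0.58 and 0.44 for f = 50%, 30% and 20%) therefore tests a claim the plan does not make, and a continuous predictor with r = 0.3 would still have 0.88.
- A reader might infer that new-site donors will have no perioperative data. The section 3 table places them under Aim 1, Appendix D allows upload or new entry, and the Appendix A footnote excludes laboratory tests and visits but not chart abstraction. Against that, Appendix D puts them outside the core protocol. The question is open.
- A reader might infer that 600 is wrong throughout. Table 1 collects demographic items from everyone, and the prevalence and course objectives are not restricted to donors followed since donation.

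**Conclusion.** The effective sample stated for risk-factor associations is wrong for pre-donation ambivalence and motivation: it is at most about 300, not 600, and 255 to 270 after expected attrition. It is an upper limit, since section 2.4 reports poor response rates in the earlier HRQOL surveys. Perioperative complications fall under the same limit through the wording of the objective; whether the data could exist for new-site donors is unresolved.

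The effect on power is moderate and conditional. On the smaller base, the 50%-loss statement holds for a binary factor split evenly (0.86), narrowly misses at 30% and fails at 20% (0.68). The correction statement at 15% attrition holds at 30% (0.86) and fails at 20% (0.73). These figures depend on d = 0.5, Bonferroni over five domains and illustrative prevalences. The finding that the base is about 300 depends on none of them.

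**What to change.** In section 4.3.3:

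1. State that for pre-donation predictors the effective sample is at most 300 donors, 255 to 270 after expected attrition. Keep 600 for prevalence, course and demographic predictors.
2. Restate power at that size and name the effect size, risk-factor prevalence and correction used. Under the assumptions above: above .80 for moderate effects at expected attrition for factors present in 20% or more without correction; after correction, only for factors present in about 30% or more, or for continuous predictors.
3. Drop the 50%-loss statement for this objective, or limit it to near-balanced or continuous predictors.
4. Reconcile the section 3 aims table (new-center prior donors under Aim 1) with Appendix D (not in the core protocol), so that it is clear whether perioperative complications will be collected for the new-site donors.

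The cost is a few restated sentences and one consistency check. Items 1 to 3 change neither enrolment nor the surveys; the stated power becomes less favourable for uncommon risk factors.
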